3.3 Secondary Study Endpoints

Secondary endpoints include LOS, the incidence of POI, and use of PCA

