5.8 Masking/Blinding of Study

The study will not be blinded.

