7.2 Sample size

The two primary endpoints of interest are pain scores over 48 hours post-surgery and the amount of narcotic medication used, standardized to OME, over 48 hours post-surgery. The pain score endpoint will be summarized as area under the curve (AUC), normalized for the total time of observation. A sample size of 100 patients per arm provides 80% power to detect an effect size of 0.40 using a two group t-test with a 0.05 two-sided significance level. The effect size is the expected difference in the mean AUCs divided by the within group standard deviation. A difference of 0.5 standard deviations in pain scores has been demonstrated to be clinically meaningful in the QOL literature. This study is adequately powered to detect this; a sample size of 100 patients in each group has 94% power to detect a difference in the mean AUC pain scores between the two groups of 0.50 standard deviations. The narcotic medication use (standardized OME) will be the cumulative use over the 48 hour period. It is also felt that a difference of 0.4 standard deviations in the mean narcotic use (standardized to OME) between the groups is clinically meaningful.

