7.3 Analysis plans

Patient Population(s) for Analysis

The patient for the primary analysis will be all randomized patients who did not withdraw prior to the initiation of anesthesia. The numbers of patients that withdraw prior to undergoing surgery will be monitored for imbalances between the arms.

Primary analysis plan

The primary analysis will be a modified intent-to-treat analysis. This means it will be an analysis of all randomized patients who did not withdraw prior to surgery according to the arm to which they were randomized.

The mean pain scores over 48 hours will be summarized as the area under the curve (AUC) of the observed pain score (y-axis) plotted by the time it was measured (x-axis). The difference in mean AUCs of the two groups will be evaluated using a two-sample t-test. In addition, the cumulative narcotic use over the 48 hour period will be determined for each patient (standardized OME). The difference in mean standardized OME will be compared with a two-sample test. If the data are skewed, a two-sample t-test will be performed on the logged values of OME or a Wilcoxon rank sum test will be used on the untransformed data. A two-sided p-value will be declared statistically significant for each primary endpoint. This will mean that the overall two-sided level of significance for the trial will be 0.10.

In addition to looking at the summary of the pain scores and OME scores, we will also plot these values over time and determine whether there are differences at individual time points.

Secondary analysis plan

The mean length of stay will be compared between the two groups with a two-sample test. If there are no outliers, a two-sample t-test will be used. If there are outliers, a Wilcoxon rank sum test will be used. A chi-square test (or Fisher's exact test) will be used to compare the rates of POI, need for a PCI and post-operative hypotension.

Comparisons will be made between the randomized groups of the baseline variables (patient, disease, and surgical) to determine if there were any randomization imbalances. If imbalances are found, a secondary analysis will be done using linear regression and adding the variables that were not balanced between the groups.

Descriptive Statistics

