8.4 Unmasking/Unblinding Procedures

This study is not blinded.

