9.2 Source Documents

Source data is all information, original records of clinical findings, observations, or other activities in a clinical trial necessary for the reconstruction and evaluation of the trial. Source data are contained in source documents. Examples of these original documents, and data records

include: hospital records, clinical and office charts, laboratory notes, memoranda, subjects' diaries or evaluation checklists, pharmacy dispensing records, recorded data from automated instruments, copies or transcriptions certified after verification as being accurate and complete, microfiches, photographic negatives, microfilm or magnetic media, x-rays, subject files, and records kept at the pharmacy, at the laboratories, and at medico-technical departments involved in the clinical trial.

Data Management

Data will be captured in an electronic fashion via institutional database that is already developed

Data Processing

Each campus will record the same data separately; all data will be combined quarterly and interim analysis will be performed.

Data Security and Confidentiality

Access to the data will be provided to only necessary persons, those that collect the data, or need to analyze the data. Data will be stored in a password-protected folder behind the Mayo firewall. All data collection and analysis will be done behind the firewall.

Data Quality Assurance

All data will be entered by appropriately trained personnel, and 1 in 50 records will be "biopsied" for correct data collection.

Data Clarification Process

Incomplete, or erroneous data will be corrected by analyzing the original patient electronic record.

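### Length of stay: the test is picked by an undefined outlier check and ignores the randomisation strata; name one stratified test in advance

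*Combined protocol and SAP*

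**What the plan says.** Section 3.3 places LOS among the secondary endpoints: "Secondary endpoints include LOS, the incidence of POI, and use of PCA". The secondary analysis plan in section 7.3 opens with the quantity to be compared, "The mean length of stay will be compared between the two groups with a two-sample test", and then makes the test conditional on the data: "If there are no outliers, a two-sample t-test will be used. If there are outliers, a Wilcoxon rank sum test will be used".

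Nothing in the document gives a cut-off for an outlier, says whether outliers are judged in the pooled data or by arm, says who judges them, or says that the choice is made before results are seen. No effect measure or confidence interval is named for LOS.

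Sections 5.3 and 7.1 stratify the randomisation by type of surgery (MIS or open) and by site. The LOS analysis in section 7.3 uses neither factor. Two other facts bear on the point. The trial is open-label (section 5.8: "The study will not be blinded"), and section 9.2 says that "all data will be combined quarterly and interim analysis will be performed".

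**The concern.** There are three weaknesses.

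- **Undefined trigger.** Common definitions of an outlier can send the same data to different tests. Whoever applies the rule has room to choose, and the document does not separate that person from the results.
- **Shifting target.** The plan promises a comparison of means. The Wilcoxon branch does not compare means, so a single extreme stay can change what is tested.
- **Strata ignored.** If open surgery means longer stays, the variation between surgery types sits in the error term of an unstratified test. The randomisation has already balanced that variation between arms. The test is then conservative and loses power.

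At stake is the error rate, power and interpretation of the first-listed secondary endpoint. The primary endpoints are not affected by this sentence.

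**Working it through.** **The plan's own figure.** Section 7.2 states power for the primary endpoints only: "A sample size of 100 patients per arm provides 80% power to detect an effect size of 0.40". The stated level there is two-sided 5%. With power = Φ(d·√(n/2) − 1.96) and n = 100, √50 = 7.071:
- d = 0.40: Φ(2.828 − 1.96) = Φ(0.868) = 80.7% (exact t: 80.4%)
- d = 0.50: Φ(3.536 − 1.96) = Φ(1.576) = 94.2% (exact t: 94.0%)

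Both stated figures (80% and 94%) reproduce. No power figure is given for LOS.

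**Inputs for LOS.** The sample size is 100 per arm (section 7.2) to 113 per arm (half of the 226 in the Study Summary). The documents give no LOS distribution, so every distribution below is an assumption.

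**Step 1: the outlier rule.** Simulation with 20,000 trials per setting, 100 per arm, stays in whole days, lognormal with median 4 days, no true difference, no strata effects, outliers judged on pooled data:

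| log-SD | Outlier found: 1.5×IQR | 3×IQR | 3 SD | t and Wilcoxon disagree at 0.05 | Smaller p-value taken |
|---|---|---|---|---|---|
| 0.3 | 70% | 5% | 87% | 2.6% | 6.4% |
| 0.5 | 99.8% | 68% | 99% | 3.5% | 6.4% |
| 0.7 | 100% | 93% | 100% | 4.6% | 7.1% |

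- The branch taken depends on the missing definition: an outlier is found in about 5% to 100% of trials.
- With any one of the three definitions fixed and followed, the type I error is about 4.7-5.2%.
- Taking the smaller p-value gives 6.4-7.1% here, and up to 7.7% at 113 per arm with log-SD up to 0.9.
- Power under an assumed 15% shorter stay (continuous lognormal, log-SD 0.5, 100 per arm) is 60.8% for always-Wilcoxon. For the rule it is 60.8% with 1.5×IQR or 3 SD and 60.1% with 3×IQR. For always-t it is 57.9%.

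**Step 2: the ignored strata.** Assume a share p = 0.30 of open surgery, balanced between arms by the stratified randomisation. Let open surgery add δ log units to the stay, and let σ be the within-stratum log-SD. An approximation on the log scale shows the mechanism. The difference between arms varies according to σ², but an unstratified test estimates the variance as σ² + p(1 − p)δ². It therefore demands Z > 1.96·k, where k = √(1 + p(1 − p)δ²/σ²) and p(1 − p) = 0.21. Take 100 per arm and a true shift of 0.35σ, so that the expected Z is 0.35 × 7.071 = 2.475. A test that accounts for the strata then has power Φ(2.475 − 1.96) = Φ(0.515) = 69.7%.

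- δ = 0.5, σ = 0.4: k = √(1 + 0.21 × 0.25/0.16) = √1.328 = 1.152, and the threshold is 2.259. Type I error = 2Φ(−2.259) = 2.4%. Power = Φ(2.475 − 2.259) = 58.6%, a loss of 69.7 − 58.6 = 11.1 points.
- δ = 0.3, σ = 0.6: k = √(1 + 0.21 × 0.09/0.36) = √1.0525 = 1.026, and the threshold is 2.011. Type I error = 2Φ(−2.011) = 4.4%. Power = Φ(2.475 − 2.011) = 67.9%, a loss of 1.8 points.

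Simulation of the planned rule against a van Elteren test (δ 0.3-0.5, σ 0.4-0.6, 100-113 per arm) agrees. The planned test rejects about 2.5-4.7% under no difference, and the stratified test about 5%. The power gain is about 1-11 points. For example, at 113 per arm with the 1.5×IQR definition, 10,000 trials per setting and the same 0.35σ shift, power is 60.3% planned and 71.3% stratified for δ = 0.5, σ = 0.4. For δ = 0.3, σ = 0.6 it is 70.7% and 72.4%. With δ = 0 the two are equal within simulation error. No site effect was modelled.

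**The case against.** The best defence is that the written rule is harmless. The plan names a trigger and one test for each branch; it does not permit running both tests and reporting the better one. Stays are probably right-skewed, so most definitions would lead to the Wilcoxon test anyway. Step 1 bears this out: followed mechanically, the rule does not inflate error and costs almost no power against always-Wilcoxon. This part stands, and it rules out three stronger readings that a reader might infer.

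- **That the plan inflates the false-positive rate.** The 6.4-7.7% is a worst case for an analyst who takes the more favourable test. The text does not license that.
- **That LOS would be tested with the weak power of a t-test on skewed data.** At log-SD 0.9 and 113 per arm the t-test alone has about 58% power for a 0.35 log-SD shift. Both the 1.5×IQR and 3×IQR rules then find an outlier in over 99% of trials, so 58% is not the power of the planned procedure.
- **That the open-label design puts arm labels before the person choosing the test.** Sections 5.8 and 8.4 ("This study is not blinded") concern treatment masking. The documents do not say whether that person sees arm labels, nor whether the quarterly interim analysis covers LOS.

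It can also be said that the t-test branch is legitimate, since the t-test holds its level at these sample sizes and the plan speaks of means. That is fair. It supports naming a comparison of means in advance, and does not support leaving the choice to the data.

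Finally, section 7.3 adds a secondary regression for unbalanced baseline variables. This does not cover the strata: stratified randomisation should keep them balanced, so the trigger for adjustment would normally not fire. The loss in step 2 arises when the strata are balanced.

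**Conclusion.** The point holds in a limited form. The LOS test depends on an undefined look at the data, the tested quantity changes with the branch, and the randomisation strata are left out. The undefined trigger is a gap in specification. At worst it raises false positives from 5% to about 6.4-7.7%, and by nothing material if one definition is fixed and followed on pooled data.

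The more substantive cost is the unstratified test: a true level of about 2.5-4.7% and a loss of about 1-11 points of power. That range rests on assumptions that the documents neither give nor contradict: 30% open surgery, stays longer by 0.3-0.5 log units after open surgery, log-SD 0.4-0.6 and 100-113 per arm. If surgery type does not affect stay, that cost disappears and the stratified test loses essentially nothing.

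The severity is low because LOS is a secondary endpoint.

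**What to change.** In section 7.3, delete the outlier rule for LOS and name one test: a Wilcoxon rank sum test stratified by site and MIS/open (van Elteren), two-sided, with a Hodges-Lehmann difference and 95% CI. Keep the mean, SD and median that the Descriptive Statistics paragraph already provides.

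The change takes one or two sentences and needs no extra patients or data. The price is that the mean difference is no longer the tested quantity. If the sponsor wants to test means, for example because mean stay bears on bed use, pre-specify a comparison of means adjusted for the same two factors. Either choice removes the data-driven switch and uses the strata.

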7.1 Randomization

Patients will be randomized in a 1:1 fashion. There will be two stratification factors: type of surgery (MIS vs. open surgery) and site (Jacksonville versus Rochester). Randomization will be performed with an online system and will use dynamic allocation..

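### The only covariate-adjusted analysis is triggered and filled by chance baseline imbalance; its covariates, including the stratification factors, should be named in advance

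*Combined protocol and SAP*

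**What the plan says.** Section 7.3 gives unadjusted primary comparisons. For pain: "The difference in mean AUCs of the two groups will be evaluated using a two-sample t-test". For opioid use: "The difference in mean standardized OME will be compared with a two-sample test", moving to logged values or a Wilcoxon test if the data are skewed.

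The secondary analysis plan in the same section then says: "Comparisons will be made between the randomized groups of the baseline variables (patient, disease, and surgical) to determine if there were any randomization imbalances". The next sentence supplies the adjustment rule: "If imbalances are found, a secondary analysis will be done using linear regression and adding the variables that were not balanced between the groups". No covariate is named, no criterion for imbalance is given, and the outcome of the regression is not stated.

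Section 7.1 says: "There will be two stratification factors: type of surgery (MIS vs. open surgery) and site (Jacksonville versus Rochester". Neither factor is named in any analysis model.

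**The concern.** With sound randomisation, a baseline difference between the arms arises by chance. Its size says nothing about whether the variable predicts pain or OME. A rule that adjusts for whatever differed can therefore bring in irrelevant variables, leave out strong predictors that happened to balance, or produce no adjusted analysis at all. The model cannot be known before the data are seen, and the missing criterion leaves further discretion in a trial that Section 5.8 says is not blinded.

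The rule also works against the most obvious candidates. Type of surgery and site were judged important enough to stratify on. Balancing them is the purpose of either allocation method that the protocol names (permuted blocks in the Study Summary, dynamic allocation in Section 7.1), so an imbalance rule will seldom select them.

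At stake are the credibility and precision of the adjusted estimate.

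**Working it through.** **Inputs from the documents.** Section 7.2: "A sample size of 100 patients per arm provides 80% power to detect an effect size of 0.40 using a two group t-test". The planned test is two-sided at the 5% level. The effect is standardised, so the SD is 1. The same section gives 94% power at 0.50 SD.

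**Assumed inputs (not in the documents).** The share of outcome variance explained by covariates (R2), the number of baseline variables, their independence, and an imbalance criterion of p<0.05.

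**1. Reproduce the plan's power.** Power = Φ(δ / (σ√(2/n)) − 1.96).
- δ = 0.40: 0.40/√0.02 = 2.828; Φ(0.868) = 80.7%. The noncentral t with 198 df gives 80.4%. Stated: 80%.
- δ = 0.50: 0.50/√0.02 = 3.536; Φ(1.576) = 94.2%. The noncentral t gives 94.0%. Stated: 94%.

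Both stated figures reproduce for the unadjusted test.

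**2. How often would chance trigger the rule?** With k independent variables, P(at least one imbalance) = 1 − 0.95^k: 22.6% for k = 5, 40.1% for k = 10, 64.2% for k = 20.

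Suppose 10 variables are compared and 2 are prognostic:
- a prognostic variable is selected: 1 − 0.95² = 9.75%
- only non-prognostic variables are selected: 0.95² × (1 − 0.95⁸) = 30.4%

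Simulation agreed, at about 10% and 30%.

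**3. What would pre-named covariates give?** Use the formula in step 1 with σ = √(1 − R2), n = 100 and δ = 0.40.

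| Assumed R2 | Power, pre-named covariates | n per arm for 80% power |
|---|---|---|
| 0 (unadjusted) | 80.7% | 99 |
| 0.05 | 82.7% | 94 |
| 0.10 | 84.6% | 89 |
| 0.20 | 88.5% | 79 |
| 0.30 | 92.2% | 69 |

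Example, R2 = 0.30: 2.828/0.8367 = 3.381; Φ(3.381 − 1.96) = Φ(1.421) = 92.2%.

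**4. What does imbalance-selected adjustment give?** Simulation used 10,000 trials per setting, 100 per arm, and 10 independent normal variables of which 2 were prognostic. The unadjusted test was used when nothing was selected. The standard error of a power near 80% is √(0.8 × 0.2/10,000) = 0.4 points.

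| Assumed R2 | Unadjusted | Imbalance-selected | Pre-named | Type I error, imbalance-selected |
|---|---|---|---|---|
| 0.10 | 80.8% | 80.6% | 84.1% | 4.7% |
| 0.30 | 80.0% | 81.2% | 91.9% | 4.4% |
| 0.50 | 80.5% | 82.3% | 97.8% | 3.6% |

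A separate run at R2 = 0.05, 0.10, 0.20 and 0.30 gave 79%, 80%, 81% and 82% for imbalance-selected adjustment, against 81%, 84%, 88% and 92% for pre-named covariates. The simulated 81% and the formula's 82.7% bracket the low end of the gain.

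**5. The stratification factors.** If these alone explained a share R2 of the variance and were almost exactly balanced, the unadjusted test would overstate its standard error. Its type I error would be 2[1 − Φ(1.96/√(1 − R2))], which is 3.9% at R2 = 0.10 and 2.8% at 0.20. Its power would be Φ(0.868/√(1 − R2)), which is 82% and 83%, against 85% and 88% with adjustment (step 3). The unadjusted test would thus be conservative.

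**The case against.** The strongest reply is that the rule governs only a secondary analysis. Both primary endpoints have stated unadjusted comparisons, and their planned power reproduces. That stands. A reader might infer that the trial loses power or falls short of its 80%; it does not.

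A reader might also infer more false positives from choosing a model on the data. In the simulations the imbalance-selected strategy stayed at or below the nominal 5%.

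The text speaks of comparisons and gives no test or threshold. It would go too far to say that the plan prescribes significance tests of baseline variables, and the 40% and 64% figures hold only under the assumed p<0.05 and independent variables. The selection depends on the data under any criterion.

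Baseline comparisons also have a legitimate use here. The trial is open-label, Section 4.4.1 allows withdrawal up to induction, and Section 7.3 excludes patients who withdraw before anaesthesia. Selective withdrawal could cause imbalance that is not due to chance. That is a reason to show baseline data by arm, but not to let those data choose the covariates.

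Finally, one might read the reference to surgical variables as allowing adjustment for intraoperative measurements. Sections 1.4, 5.2 and 5.5 place both injections before the operation, so such measurements would follow treatment. But Section 7.3 limits the comparison to baseline variables and names none measured after injection. This is a possible reading to close off, not a demonstrated error.

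**Conclusion.** The concern holds as a weakness in the plan's only adjusted analysis. Whether that analysis is run, and what it contains, depend on chance differences between the arms, and it is likely to omit the two stratification factors. The stated 80% and 94% power and the type I error of the primary tests are not harmed.

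The loss is a forgone gain at 0.40 SD. By formula it is 82.7 − 80.7 = 2.0 points at R2 = 0.05 and 92.2 − 80.7 = 11.5 points at R2 = 0.30. The simulations put the low end nearer 81%. These R2 values are assumptions: nothing in the documents shows how strongly any covariate predicts pain or OME. The formulas and simulations also treat the outcome as roughly normal, so for OME they apply only on a scale where that is reasonable.

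The gain belongs to whichever analysis carries the adjustment. If the adjusted model stays a supporting analysis, the test that decides the trial is no more powerful than before. This is worth changing because it is cheap, not because the trial's conclusion is at risk.

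**What to change.** Replace the imbalance-triggered regression in Section 7.3 with one pre-specified linear model for each of the two primary endpoints (pain AUC, cumulative OME), fitted whatever the observed balance.

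- **Terms:** arm, site, planned approach (MIS or open, as randomised), and named pre-randomisation variables. Age and BMI are eligibility items in Section 4.1. Sex can be added if it is collected; the documents do not list it.
- **Exclusions:** state that no variable measured after the study injection enters the model.
- **OME scale:** fix it in advance, for example logged if skewed by a stated criterion.
- **Role:** say whether the model is the primary or the key supporting analysis. If primary, Section 7.2 needs a matching sentence, since its sample size rests on the unadjusted t-test.
- **Baseline data:** keep summaries by arm as description only, including as a check on withdrawals before anaesthesia, and do not use them to choose covariates.

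The cost is protocol and SAP wording. No extra patients are needed, and the core covariates are already recorded for stratification or eligibility. The change should be made before outcome data by arm are examined.

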7.5 Data Collection

Data will be captured in an electronic fashion via institutional database that is already in use for the Rochester site. A REDCap database will be used to capture the information at the Jacksonville site and to capture adverse event (complication) data from both sites. The same definition of variables will be used at both sites.

8 Safety and Adverse Events

8.1 Definitions

Unanticipated Problems Involving Risk to Subjects or Others (UPIRTSO)

Any unanticipated problem or adverse event that meets the following three criteria:

- Serious: Serious problems or events that results in significant harm, (which may be physical, psychological, financial, social, economic, or legal) or increased risk for the subject or others (including individuals who are not research subjects). These include: (1) death; (2) life threatening adverse experience; (3) hospitalization, readmission, or prolonged hospital stay; (4) disability/incapacity - persistent or significant; (5) birth defect/anomaly; (6) breach of confidentiality and (7) other problems, events, or new information (i.e. publications, DSMB reports, interim findings, product labeling change) that in the opinion of the local investigator may adversely affect the rights, safety, or welfare of the subjects or others, or substantially compromise the research data, **AND**
- Unanticipated: (i.e. unexpected) problems or events are those that are not already described as potential risks in the protocol, consent document, not listed in the Investigator's Brochure, or not part of an underlying disease. A problem or event is "unanticipated" when it was unforeseeable at the time of its occurrence. A problem or event is "unanticipated" when it occurs at an increased frequency or at an increased severity than expected, **AND**
- Related: A problem or event is "related" if it is possibly related to the research procedures.

Adverse Event

An untoward or undesirable experience associated with the use of the medications used in this trial, as bellow:

- Any arrhythmia/ tachycardia/bradycardia necessitating intervention (medicine or cardioversion)
- Vertigo, tinnitus, seizure
- Any myocardial infarction
- Any site infection / hemorrhage / persistent injection site pain, neuropathy or nerve injury
- Postoperative headaches

Serious Adverse Event

Adverse events are classified as serious or non-serious. Serious problems/events can be well defined and include;

- Death
- Life threatening adverse experience
- Hospitalization
- Inpatient, new, or prolonged; disability/incapacity
- Persistent or significant birth defect/anomaly

and/or as per protocol there may be problems/events that in the opinion of the sponsor-investigator may have adversely affected the rights, safety, or welfare of the subjects or others, or substantially compromised the research data.

Other important medical events are those that may not be immediately life threatening, but are clearly of major clinical significance. They may jeopardize the subject, and may require intervention to prevent one of the other serious outcomes noted above. For example, drug overdose or abuse, a seizure that did not result in in-patient hospitalization or intensive treatment of bronchospasm in an emergency department would typically be considered serious.

All adverse events that do not meet any of the criteria for serious, should be regarded as **non-serious adverse events**.

Adverse Event Reporting Period

For this study, the study treatment follow-up period is defined as 30 days following the last administration of study treatment.

Preexisting Condition

A preexisting condition is one that is present at the start of the study. A preexisting condition should be recorded as an adverse event if the frequency, intensity, or the character of the condition worsens during the study period.

General Physical Examination Findings

At screening, any clinically significant abnormality should be recorded as a preexisting condition. At the end of the study, any new clinically significant findings/abnormalities that meet the definition of an adverse event must also be recorded and documented as an adverse event.

Post-study Adverse Event

All unresolved adverse events should be followed by the sponsor-investigator until the events are resolved, the subject is lost to follow-up, or the adverse event is otherwise explained. At the last scheduled visit, the sponsor-investigator should instruct each subject to report, to the sponsor-investigator, any subsequent event(s) that the subject, or the subject's personal physician, believes might reasonably be related to participation in this study.

Hospitalization, Prolonged Hospitalization or Surgery

Any adverse event that results in hospitalization or prolonged hospitalization should be documented and reported as a serious adverse event unless specifically instructed otherwise in this protocol. Any condition responsible for surgery should be documented as an adverse event if the condition meets the criteria for an adverse event.

Neither the condition, hospitalization, prolonged hospitalization, nor surgery are reported as an adverse event in the following circumstances:

- Hospitalization or prolonged hospitalization for diagnostic or elective surgical procedures for a preexisting condition. Surgery should **not** be reported as an outcome of an adverse event if the purpose of the surgery was elective or diagnostic and the outcome was uneventful.
- Hospitalization or prolonged hospitalization for therapy of the target disease of the study, unless it is a worsening or increase in frequency of hospital admissions as judged by the clinical investigator.

